1.3 Rationale

Anastrozole is available as a 1 mg film-coated tablet. The registered dose is a daily tablet, daily for five years in the absence of intolerable side-effects or recurrence of disease. Anastrozole is highly effective in inhibiting in vivo aromatization. Pharmacodynamic data from Phase I clinical studies in postmenopausal female volunteers and patients with advanced

breast cancer demonstrate maximal suppression of plasma estrogens occurring after 3-4 days of anastrozole treatment (0.5-1.0 mg) and no recovery in estradiol was apparent for up to 144 hours after the last dose [16, 17, 18]. Thus individual cases of missed tablets are not expected to translate into meaningful biological or clinical effects. However, the most important requirement for the effectiveness of an oral therapy self-administered without medical supervision is optimal compliance i.e. the extent to which a patient adheres to the recommended therapy. Rates of compliance for different therapies of chronic diseases are reported in the literature, vary widely and irrespective of disease are low, not exceeding 40-50% within a few months after beginning of treatment [19]. Only a few reports have evaluated the rate of compliance in the adjuvant therapy of breast cancer. Usually patients with the potential to become non-compliant are not excluded from randomised clinical study participation. A common withdrawal criterion is failure to comply with the protocolled dosing schedule by less than 80%.

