7. PROGRAM PLAN AND PROCEDURES

7.1 Overall design and flow chart

This is an open, multicentre NIS.

[figure not shown]
It is planned to enrol subjects into this NIS between Q1 2009 and Q1 2010. Based on the plan outlined below, it is assumed that the last subject will be enrolled in Q1 2010 and subsequently documented until Q4 2010.

The treatment with anastrozole can be stopped at any time.

Furthermore it is expected, that the last completed eCRF will be filled in Q4 2010. It is planned to close all centres until end of Q1 2011 (i.e. the fees for all participating centres are paid).

Treatment with Anastrozole

Study duration

*or at point of treatment discontinuation

Evaluation period

Information to patients: study start, weeks 1, 3, 5, 8, 12, 20

- 1 The start of the adjuvant treatment with anastrozole is defined by the date of the first tablet intake. If this date is not available, the date of first prescription will be taken.
- 2 The end of participation in this NIS is defined as recurrence or death or withdrawal of informed consent is documented via WBDC. Patients who stop endocrine therapy (i.e. do not take further treatment) or patients who switch to an adjuvant endocrine therapy with tamoxifen or a different aromatase inhibitor or patients considered 'lost to follow-up' (i.e.: can no longer be contacted) will be documented as premature terminations. Otherwise this NIS terminates after completion of 12 (15) months observation period (12 respectively 15 months observation period results from time slot for inclusion, minimum 3 and maximum 6 months of anastrozole therapy prior to enrolment)

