8.1.3 Documentation after 3, 6, and 9 months after study start

The following patient data should be documented after 3, 6, and 9 months after study start or at the time point of treatment discontinuation:

Observation interval	Date of last examination Date of documentation (current date)
Date of observation	
Patient lost to follow-up status	If the patient does not attend follow-up visits, can she be contacted (yes, no – lost to follow-up)
Demographics	Weight (kg)
Occurrence of adverse events	(no, yes) ⇒ AE/SAE-module
Status of breast cancer disease	Loco-regional recurrence / contralateral recurrence / distant metastasis (if yes: date of recurrence / localisation?)
Survival status	(alive, died) ⇒ Survival –module
Continuation of anastrozole therapy (yes, no)	Yes ⇒ Treatment continuation-module No ⇒ Treatment discontinuation module Change of endocrine therapy ⇒ Switch module
Patient continuation of participation in COMPACT	(Yes, no – consent withdrawn, no – died, no – other reasons) ⇒ Consent withdrawal-module
Concomitant medication	No, yes => please specify

The following data should be documented after 3, 6, and 9 months of endocrine therapy or at the time point of treatment discontinuation as indicated and applicable by patient's status:

Treatment continuation – Module (continuation of anastrozole therapy)	
Treatment compliance: doctor's assessment	Estimation of compliance by doctor's judgement: "How many tables have been taken in the observed period?" (none, few, less than half, appr. half, more than half, almost all, all)
Number of medicines / tablets or capsules per day	
Anastrozole prescriptions / sample packages	Number and package size
Was anastrozole intake stopped / taken irregularly?	if yes => reason?
Concomitant medication	No, yes => please specify

Arthralgia – Module (to be filled in in case of arthralgia occurrence during anastrozole therapy)	
Arthralgia questionnaire	
Arthralgia onset during anastrozole therapy (no, yes, unknown – if yes : localisation, swelling, pain intensity; duration, relationship to study drug)
 
Therapy of arthralgias: no, yes – please specify.
 
Assessment of treatment with medication (drug name, dose, package size, duration (start-end))
 
Doctor's visits (including doctor's specification)
 
Diagnostics? if yes => specify
 
Physiotherapy? if yes => specify
 
Adjuvants? if yes => specify
 
Lifestyle changes? if yes => specify

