8.3.1.2 Documentation of AE

All adverse events occurring during the observational period should be documented on the corresponding subject-related AE CRFs. However, events and symptoms which are related to a worsening of the underlying disease to be treated with anastrozole should not be documented as AE.

For each AE, the following information should be given:

- description of adverse event,
- start date of AE,
- stop date of AE,
- maximum intensity of AE [mild, moderate, severe],
- action taken on anastrozole [none, dose reduction, temporarily stopped, stopped],
- outcome [recovered, not yet recovered, permanent disability, death, unknown],
- causality/relationship to anastrozole [no, yes],
- AE serious [no, yes]

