11. STATISTICAL METHODS AND DETERMINATION OF SAMPLE SIZE

The statistical analysis and reporting of this NIS will be performed by DSH statistical services under the supervision of and in close collaboration with AstraZeneca GmbH.

This section is focused on the first statistical analysis, i.e. after all patients were observed for at least three months. The final statistical analysis (after all patients were observed for 9 months) will be performed in the same way, but using the data in a cumulative way.

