11.1 Statistical evaluation – general aspects

A comprehensive Statistical Analysis Plan (SAP) covering details of all methods used to analyze the various parameters will be prepared before database lock of the 3 months data. The SAP will be reviewed, and if needed, updated before this first data base lock.

The disposition of patients with regard to

- the number of patients enrolled,
- the number of patients treated with anastrozole (upfront and following two to three years of tamoxifen treatment),
- the number of patients who discontinued prematurely from the anastrozole therapy within the study period,
- the number of patients who discontinued prematurely from this NIS within the present observational period,
- the number of patients who completed the NIS up to 3, 6, and 9 months after study start,
- the number of patients who are still taking anastrozole up to the time point of the present statistical analysis of this NIS

will be displayed by specialized clinic (including overall). The disposition of the patients in the subsequent final analysis will be displayed in the same way.

Patients without any documented start of an endocrine therapy (e.g. missing information on prescriptions) will be excluded from all statistical analyses, but will be displayed in all data listings.

All treated patients who discontinued prematurely from the anastrozole therapy and/or the NIS (according to the corresponding CRFs) will be listed by clinic; at least the time-point of discontinuation, the main reason for discontinuation and relevant data of exposure to anastrozole will be presented.

The following text refers to more general statistical key-principles based on the statistical analysis data sets, i.e. the intent-to-treat population and the safety population:

Binary, categorical and ordinal parameters will be summarized by means of absolute and percentage numbers (including ‘missing data’ as valid category at Visit 1). Numerical data will be summarized by means of standard statistics (i.e. number of available data, mean, standard deviation, minimum, median, maximum, lower and upper quartile). Wherever useful, the summary statistics will be presented by specialized clinic (including overall) and/or visit.

In addition, adequate figures (e.g. bar charts, Box-Whisker-Plots) may be presented to summarize the results for some parameters also in a graphical way.

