11.4.1 Outcome variables

The objectives outlined in chapter 3 will be analysed as follows:

Primary objective:

Assessment of arthralgia scores and patients' compliance within the first year of anastrozole treatment¹, stratified by upfront and switch therapy as well as assessment of the relationship between compliance and arthralgia scores.

The absolute number and percentage of compliant patients will be calculated. Groups will be compared with Fisher's exact test

From the arthralgia scores an overall score will be calculated (sum of 14 single item scores divided by 14). Groups will be compared using t-test.

Relationship between compliance and arthralgia scores will be assessed using logistic regression analysis.

Of primary interest are the 3 months data (data obtained within the first three months of anastrozole therapy). Secondly, the other time points will be evaluated.

Secondary objectives:

Incidence of arthralgias and arthralgia characteristics within the first year of anastrozole therapy¹ stratified by upfront and switch therapy and assessment of the relationship of arthralgia incidence and arthralgia characteristics to patients' compliance.

The absolute number and percentage of patients with at least one event of arthralgia within pre-defined intervals (0-3, 3-6, 6-9, 9-12 and 12+ months after the start of anastrozole treatment) will be calculated.

Characteristics of arthralgias within each time interval will be evaluated descriptively stratified by upfront and switch therapy:

- Maximum intensity, localization, relationship to study drug, diagnostics and arthralgia management presenting number and percentage of each category.
- Time between start of anastrozole therapy and first incidence of arthralgia will be analysed using the Kaplan-Meier method.

Maximum duration of arthralgias will be evaluated descriptively, presenting standard statistics.

Retrospective assessment of incidence of pre-existing arthralgias before start of anastrozole treatment, stratified by upfront and switch therapy.

The absolute and percentage number of patients with pre-existing arthralgias will be calculated stratified by upfront and switch therapy.

Descriptive assessment of arthralgia therapy and of costs of arthralgia therapy, stratified by upfront and switch therapy.

Evaluation will be performed descriptively with standard statistics and associated with cost modules of sick funds.

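### Maximum arthralgia duration is summarised with ordinary statistics that cannot handle episodes still ongoing when observation ends

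*Protocol*

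**What the plan says.** Protocol section 11.4.1, under the secondary objective on arthralgia incidence and characteristics, fixes the method for duration: "Maximum duration of arthralgias will be evaluated descriptively, presenting standard statistics". Section 11.1 says what that means, since numerical data are "summarized by means of standard statistics (i.e. number of available data, mean, standard deviation, minimum, median, maximum, lower and upper quartile". None of these summaries takes account of censoring.

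For the neighbouring time variable, the same part of section 11.4.1 chooses a censored-data method: "Time between start of anastrozole therapy and first incidence of arthralgia will be analysed using the Kaplan-Meier method". Time to progression is also to be analysed by Kaplan-Meier.

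On data collection, the arthralgia module in section 8.1.3 lists "localisation, swelling, pain intensity; duration, relationship to study drug", with no instruction for an episode that has not ended. The adverse event form in section 8.3.1.2 does foresee this case: "outcome [recovered, not yet recovered, permanent disability, death, unknown". It also asks for start and stop dates.

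On follow-up, section 7.1 states: "Otherwise this NIS terminates after completion of 12 (15) months observation period". Section 7.6 makes stopping or switching endocrine treatment a reason to leave the programme.

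**The concern.** Duration of an episode is right-censored whenever observation ends before the episode does, and the design makes this possible in three ways: the scheduled last visit, treatment stop or switch, and drop-out. Exposure normally continues after the last visit, because section 1.3 says: "The registered dose is a daily tablet, daily for five years".

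Ordinary statistics leave two choices for an ongoing episode. It can be cut at the last documentation and counted as if it had ended there, or it can be left out. The protocol does not say which. Cutting makes the mean too low. Leaving ongoing episodes out removes the long ones selectively and lowers both mean and median.

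Duration is a listed arthralgia characteristic, and section 11.4.1 names it among the candidate factors for compliance. A figure limited by the study's own length could be read as showing that arthralgia is short-lived.

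**Working it through.** The protocol gives no figure for duration, so there is nothing to reproduce. The check asks how far ordinary statistics can go wrong under the protocol's follow-up.

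**Inputs from the protocol.** Entry is 3 to 6 months after the start of anastrozole, with last documentation 9 months later. End of observation is therefore 3 + 9 = 12 to 6 + 9 = 15 months (sections 6 and 7.1). The first analysis takes place "i.e. after all patients were observed for at least three months", so follow-up then reaches 3 + 3 = 6 to 6 + 3 = 9 months.

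**Assumptions, not in the protocol.** One episode per patient; exponential duration with median m of 1, 3, 6 or 12 months; onset uniform over months 0 to 12; end of observation uniform over months 12 to 15; no earlier drop-out.

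**Share ongoing.** With rate λ = ln 2 / m, the share is the product of two averages:

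share = [(2^(−12/m) − 2^(−15/m)) / (3λ)] × [(2^(12/m) − 1) / (12λ)]

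- m = 6: (0.2500 − 0.1768)/0.3466 × 3/1.3863 = 0.2113 × 2.164 = 0.457
- m = 3: (0.0625 − 0.03125)/0.6931 × 15/2.7726 = 0.0451 × 5.410 = 0.244
- m = 1: (0.00024414 − 0.00003052)/2.0794 × 4095/8.3178 = 0.0001027 × 492.3 = 0.051

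**Mean if ongoing episodes are cut.** For exponential durations this equals (m / ln 2) × (1 − share), so the relative shortfall equals the share ongoing. For m = 6: 8.66 × 0.543 = 4.70. For m = 3: 4.33 × 0.756 = 3.27. For m = 1: 1.443 × 0.949 = 1.37.

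**Simulation.** 400,000 episodes per setting agree with these and add the other summaries (months):

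| True median | Ongoing | Mean: true / cut / resolved only | Median: true / cut / resolved only | Kaplan-Meier median |
|---|---|---|---|---|
| 1 | 5% | 1.44 / 1.37 / 1.31 | 1.00 / 0.98 / 0.93 | 1.00 |
| 3 | 24% | 4.33 / 3.27 / 2.76 | 3.00 / 2.58 / 2.11 | 3.00 |
| 6 | 46% | 8.68 / 4.70 / 3.54 | 6.02 / 4.00 / 2.86 | 6.02 |
| 12 | 66% | 17.30 / 5.85 / 4.05 | 12.01 / 5.34 / 3.41 | 12.03 |

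**Sensitivity.**
- Lognormal durations (log-scale standard deviation 1), true median 6: 47% ongoing; mean 9.86 reported as 4.90 or 3.99; median 6.00 reported as 4.16 or 3.40.
- Onset confined to months 0 to 6, exponential, true median 6: 31% ongoing. The cut mean is 6.03 against 8.68, but the cut median is 6.01 against 6.01. Every episode here has at least 12 − 6 = 6 months of potential follow-up, so none is cut below the true median. With resolved episodes only, the median is 3.71.
- First analysis, onset over months 0 to 6, true median 3: 39% ongoing; mean 4.34 reported as 2.64 or 1.98; Kaplan-Meier median 3.00. With a true median of 12, the Kaplan-Meier median cannot be estimated at that analysis.

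Across all settings, the share ongoing ran from about 0% to 70% at the final analysis and from about 10% to 84% at the first.

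**The case against.** The protocol sends analysis details to a statistical analysis plan that is not shown, and a rule for ongoing episodes could stand there. The objective is limited to the first year of therapy, so duration observed in that window, labelled as such and shown with the number ongoing, is a legitimate description. Both points carry weight. But the protocol does not leave the method open: it names summaries that cannot handle censoring, and it gives no such label.

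Stronger readings are tempting and are not supported:

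- **That many episodes will be ongoing.** This is an inference from the design. No episode length is documented, and with 1-month episodes the problem nearly disappears.
- **That every summary is too low.** The median of durations cut at the last visit can be correct, as the case with onset over months 0 to 6 shows.
- **That censoring is heavier for duration than for onset.** Every patient without arthralgia is censored for onset. Section 1.1 cites 35.6% joint disorders on anastrozole in the large randomised adjuvant trial. If that rate is any guide, 100 − 35.6 = about 64% would be censored for onset, against 46% for duration in the 6-month scenario.
- **That duration drives the cost results.** Section 11.2 costs the recorded diagnostic and therapeutic measures. Nothing enters arthralgia duration into costs.

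Two limits of the check also stand. The plan summarises a maximum, apparently per patient, whereas the check uses single episodes. And Kaplan-Meier does not remove all bias: joint pain is a listed reason for stopping anastrozole (section 8.1.3) and stopping treatment ends participation, so censoring at that point may be informative.

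**Conclusion.** The point holds in a limited form. The protocol fixes ordinary summaries for a quantity that can be right-censored, has no rule for ongoing episodes, and departs from its own Kaplan-Meier choice for onset and progression. The mean is too low wherever an appreciable share is ongoing, and so is the median if only resolved episodes are used. In the assumed scenarios with onset over months 0 to 12, the cut mean is about 5% too low for a 1-month true median (1.37 against 1.44), 24% for 3 months (3.27 against 4.33) and 46% for 6 months (4.70 against 8.68). These sizes rest on assumed episode lengths and onset patterns and on having no early drop-out, which would cut off further episodes.

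The consequence is confined to a secondary descriptive characteristic and to its use as a candidate factor for compliance. The co-primary analyses and the sample size are not affected.

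**What to change.** Replace the sentence on maximum duration in section 11.4.1 with wording to this effect:

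- Define one episode per patient, for example the first treatment-emergent arthralgia. Describe its duration from onset to resolution by Kaplan-Meier, by upfront and switch therapy, with ongoing episodes censored at last documentation.
- Report the number and share of episodes ongoing at last contact.
- If maximum observed duration is also shown, label it as observed within the study period and state how ongoing episodes were counted.
- Note two limitations. Censoring at treatment stop may be informative when arthralgia causes the stop. Observed duration used as a factor for compliance is itself shortened by stopping treatment, and a Kaplan-Meier curve does not repair that covariate.

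The cost is slightly more analysis work. New or worsened arthralgia meets the adverse event definition in section 8.3.1.1, the baseline form routes it to an arthralgia adverse event module, and section 8.3.1.2 requires start date, stop date and outcome. Because the follow-up arthralgia module lists only a duration item, the sponsor should confirm that the dates are captured for every arthralgia and state how an ongoing episode is entered in that item.
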